7.3 LOST TO FOLLOW-UP

A participant will be considered lost to follow-up if they fail to complete at baseline, or 12 months, the SEDM, and is unable to be contacted by the study site staff after the maximum number of reminders and contact attempts.

Before a participant is deemed lost to follow-up, the Principal Investigator or designee will make every effort to regain contact with the participant (where possible, 2 reminders via KiT intervention and email, SMS, or telephone follow-ups and, if necessary, a certified letter to the participant's last known mailing address or local equivalent methods). These contact attempts will be documented in the participant's medical record or study file. Should the participant continue to be unreachable, they will be considered to have withdrawn from the study with a primary reason of lost to follow-up.

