- 8) The local coordinator will randomize the participant using REDcap's automatic randomization feature. Both the local coordinator and participant will be aware of what study arm they were assigned to as local coordinator will need to explain next steps to the participant depending on study arm and participant will be aware of whether they will receive texts from the KiT intervention.
- 9) Upon randomization, the local coordinator will enter the randomized participant study ID number, randomization arm, mobile phone number, and preferred language in the Research Assistant Participant Enrollment form via Memotext.
- 10) Memotext will send an initial SMS to the participant's mobile phone number, letting them know they are now enrolled in KiT.
 - i. The following SMS will include the first URL link to a REDCap survey that first prompts to participant to complete the baseline KiT survey (demographic information and information about the participant's diabetes care and self-management). When this questionnaire is completed and submitted, the survey will automatically produce the next surveys for participant completion, one at a time: READDY tool questionnaire, SEDM, and BDA Stigma subscale
 1. Some of the content and sequence of the messages and resources sent to the intervention participants will be personalized, based on confidence ratings as measured by the "Readiness of Emerging Adults with Diabetes Diagnosed in Youth" (READDY) tool.
 2. For all participants, if they do not complete the questionnaires within 1 week of receipt, KiT intervention will send a follow-up reminder SMS asking them to complete the questionnaire. This reminder will be sent a maximum of two times (1 week apart). At week three, the local research coordinator will be notified via email by Memotext that the participant has not yet completed their questionnaires and will then follow up with the participant via telephone, SMS or email asking them to complete the questionnaires.
 3. Once the participant completes the questionnaires, they will be sent their \$20 Amazon gift-card via SMS.
 - ii. If the participant is in the intervention arm, after they complete the baseline questionnaires, they will then be sent an SMS with a link to a short enrollment survey where they will learn how to use KiT, access the settings, set up their frequency preferences to receive the content, and set up appointment reminders.

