7.2 PARTICIPANT DISCONTINUATION/WITHDRAWAL FROM THE STUDY

Participants are free to withdraw from participation in the study at any time upon request.

An Investigator may discontinue or withdraw a participant from the study for the following reasons:

- Withdrawal of informed consent (participant withdrew for any reason)
- Significant study intervention non-compliance
- If the participant meets an exclusion criterion (either newly developed or not previously recognized) that precludes further study participation

Participants who sign the informed consent form, and are randomized and receive the study intervention, and subsequently withdraw, or are withdrawn or discontinued from the study, will be attempted to be replaced if there are at least 12 months remaining in the study so new replacements would receive the full intervention. The data from participants who are withdrawn or discontinued from the study will be used in the analysis unless the participant requests otherwise.

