8.4 POPULATIONS FOR ANALYSES

The conventional frequentist analyses are often interpreted in a dichotomous matter, based on the p-value chosen as threshold for 'statistical significance' and 'no evidence of effect' is confounded with 'evidence of no effect'. A Bayesian analysis will be conducted to provide the probability of any benefit or harm. An intention-to-treat analysis will be conducted by blinded analysts. We will evaluate the extent of missing data to determine if values are missing at random or not and will consider imputation to account for missing values.

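### Section 7.3 classes a randomised participant who misses the baseline SEDM and cannot be reached as withdrawn, which may forfeit the 12-month primary outcome

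*Protocol*

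**What the plan says.** Protocol Section 7.3 sets a two-part trigger. The first part is "A participant will be considered lost to follow-up if they fail to complete at baseline, or 12 months, the SEDM". The second is "and is unable to be contacted by the study site staff after the maximum number of reminders and contact attempts". When both hold and further efforts fail, "they will be considered to have withdrawn from the study with a primary reason of lost to follow-up".

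The other relevant places are:

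- **Sections 5.4 (steps 8 to 10) and 6.2:** randomisation follows consent, and coordinator and participant both know the arm. The baseline questionnaires, including the SEDM, go out by SMS afterwards.
- **Section 5.4, step 10(ii), intervention arm only:** "after they complete the baseline questionnaires, they will then be sent an SMS with a link to a short enrollment survey". The intervention begins once that survey is done.
- **Section 5.4 (step 11) and the arm descriptions in Section 6.1.1:** the 6- and 12-month links go to both arms. Completing baseline is not made a condition.
- **Section 7.2:** "The data from participants who are withdrawn or discontinued from the study will be used in the analysis unless the participant requests otherwise".
- **Section 8.4:** "An intention-to-treat analysis will be conducted by blinded analysts". The team will assess missing data and "will consider imputation to account for missing values".
- **Sections 3.1 and 8.5.2:** the primary endpoint is the SEDM at 12 months, modelled with baseline SEDM as a covariate.

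**The concern.** A missed baseline form leaves a covariate missing. It does not mean that the outcome is lost. Section 7.3 nevertheless gives the two the same status, and that status is withdrawal. Because the baseline SEDM comes after allocation, the rule acts on people who are already part of the randomised comparison, at a time when their 12-month outcome could still be collected.

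At stake are the 12-month scores of the least responsive participants. If withdrawal means that no further links are sent, the gap arises at data collection, and an analysis plan can then only impute. Someone who missed the baseline package has also left the READDY, the stigma subscale and the demographic survey blank, so there would be little to impute from.

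**Working it through.** **1. Order of events.** Consent, then randomisation with the arm disclosed, then baseline questionnaires by SMS. Under Section 5.4 step 10, up to two reminders follow a week apart and the coordinator is alerted at week three. Section 7.3 adds further contact attempts without a time limit. The withdrawn status can therefore be assigned many months before the 12-month SEDM is due.

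**2. Does any passage stop the later links?** None says so. Sections 5.4 (step 11) and 6.1.1 send them to both arms, while Section 7.3 says the person has left the study without saying whether sending continues. Section 7.1 states that stopping the intervention is not leaving the study and that remaining procedures go on; Section 7.3 has no matching sentence for someone who missed baseline. Section 4.3 ties study completion to the 12-month SEDM, not to the baseline one.

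**3. The two readings.**

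- *Links continue.* A 12-month score may still arrive, Section 7.2 keeps it, and only the baseline covariate is missing.
- *Links stop.* There is neither a baseline nor a 12-month SEDM. Section 7.2 has no outcome to keep, and imputation alone can keep the person in the primary analysis.

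**4. Could the loss differ by arm?** The questionnaires, reminders and gift card are the same in both arms. The difference is that completion starts the intervention in one arm and starts nothing in the other, with the arm already known. A difference is possible, but the protocol gives neither its direction nor its size.

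**5. Size: power.** Section 8.3 claims more than 80% power for a difference of 0.75 with 117 per arm, 20% loss and alpha 5%. No SD is given, so the figure cannot be reproduced directly. Taking the test as two-sided:

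- Evaluable per arm: 117 × 0.8 = 93.6.
- Largest SD compatible with 80% power, normal approximation: 0.75 / [(1.960 + 0.842) × √(2/93.6)] = 1.83. The t-test gives 1.82.
- Power at 93 per arm for assumed SDs: 1.5 → 92%; 1.75 → 83%; 1.8 → 81%; 2.0 → 72%; 2.5 → 53%.

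Now let a further fraction *b* be lost through the baseline rule, with n per arm = 93.6 × (1 − *b*) and an assumed SD of 1.8:

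| *b* | n per arm | power |
|---|---|---|
| 0 | 93.6 | 81% |
| 5% | 88.9 | 79% |
| 10% | 84.2 | 77% |
| 15% | 79.6 | 74% |

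If these people instead count within the planned 20%, each 5% of the sample is 0.05 × 234 = 11.7 people, a quarter of the allowance of 46.8. Section 8.3 does not say which applies.

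**6. Size: bias (assumed inputs only).** If a fraction *p* of one arm has no 12-month score, would have scored *d* lower than those retained, and imputation does not recover it, that arm's mean rises by *p* × *d*. With an assumed *p* = 10% in one arm, none in the other, and *d* = 0.75 to 1.0, the shift is 0.075 to 0.10, or 10% to 13% of 0.75. Equal losses with equal deficits in both arms would cancel.

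**The case against.** A reader might infer that Section 7.3 is a post-randomisation exclusion, contradicts intention-to-treat, and turns the analysis set into a set of baseline completers. The protocol does not support that. Section 7.3 assigns a follow-up status and defines no analysis set. Section 7.2 says that withdrawn participants' data will be used, and Section 8.4 states intention-to-treat with imputation to be considered. Nothing prescribes a complete-case fit, although the primary model adjusts for baseline SEDM. This part of the objection stands in full.

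Three further points also carry weight:

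- The trigger needs non-completion and failure of every contact route. Missing the form alone is not enough, so the affected number may be small, and the protocol gives no rate.
- No passage says that the links stop, and someone unreachable by all routes may not answer at 12 months anyway.
- The arm effect and the bias figure rest on assumption, and drawing on the 20% allowance is what that allowance is for.

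What the objection leaves in place is the rule's wording. It calls a missing baseline form loss to follow-up, says the person has left the study, and does not protect the later outcome contact. Keeping data that exist does not produce a score that was never requested. The replacement clause in Section 7.2 ("will be attempted to be replaced if there are at least 12 months remaining in the study") does not help either: it is worded for people who received the intervention, and a replacement restores the head count without recovering the missing outcome.

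**Conclusion.** The point holds as a flaw in a stated follow-up rule, not as a demonstrated breach of intention-to-treat. Section 7.3 lets a missing post-randomisation baseline form, combined with unreachability, end a participant's time in the study before the primary outcome is due. This sits uneasily with Sections 5.4 and 6.1.1, which send the 12-month link to both arms without that condition.

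Whether outcomes are actually forfeited depends on an unstated matter, namely whether links stop on withdrawal. The size is unknown. The power range of 81% down to 74% assumes an SD of 1.8 and up to 15% loss beyond the planned 20%. The 0.075 to 0.10 shift assumes loss in one arm only. Neither is an estimate for this trial. This is a cheap improvement that protects primary outcome data.

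**What to change.** In Section 7.3:

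- Define loss to follow-up by the 12-month SEDM only, and record a missing baseline SEDM as a separate item.
- State that the automated 6- and 12-month links continue to everyone randomised who has not withdrawn consent, timed from enrolment as in Section 5.4 step 11, so that no baseline completion date is needed.
- State that all of these participants stay in the intention-to-treat analysis.

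How the primary model handles a missing baseline covariate can be left to the statistical analysis plan.

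The cost is a short wording change, a few extra automated messages, and some participants with a missing baseline value to handle in the model.

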8 STUDY ASSESSMENTS AND PROCEDURES

8.1 ASSESSMENTS

- **Questionnaires and patient-reported outcomes:** all the following will be sent as URLs via KiT intervention SMS that will link-out to web-based REDCap surveys:
 - KiT Demographic survey (diabetes care and self-management),

- READDY tool: transition readiness assessment for emerging adults with diabetes diagnosed in youth, administered at baseline, and 6 and 12 months after baseline
- SEDM: self-efficacy with diabetes self-management, administered at baseline, 6 and 12 months after baseline
- BDA Stigma subscale: type 1 diabetes stigma assessment subscale, administered at baseline, 6 and 12 months after baseline

- **Administrative data via OHIP or RAMQ number collection:** the following data will be collected via linking to administrative datasets via ICES in Ontario and Med-Echo and Régie de l'assurance maladie du Québec (RAMQ) databases in Quebec
 - Deprivation quintile
 - diabetes related ED visits and hospitalizations
 - HbA1c (in Ontario only)
- **Cost of implementation:** we will measure all relevant costs associated with the intervention and its implementation using study data. More specifically, costs will be collected in five broad categories: staff (e.g. salaries, fee for services), equipment (e.g. equipment/technology platform and depreciation costs, software costs, installation costs, and maintenance costs), communication (e.g. data transmission costs), administration (e.g. administration costs, supplies)
- **Process Evaluation:** The embedded three-step process evaluation will occur between 3 and 12 months after the intervention launch, contingent on sufficient participant enrollment and data collection. In Step 1, we will develop a theoretical model depicting the predictors of the initial engagement and sustained use of the KiT intervention (includes personalized educational content, Q & A, and standard educational curriculum) according to extant literature on the e-health interventions. This program theory builds on the tenants of the Health Action Process Approach (HAPA) and the Technology Acceptance Model (TAM) to generate candidate hypotheses, which have been framed using the Context-Mechanism-Outcome (CMO) configurations that are typical of realist evaluation. In Step 2, we will test the hypothesized pathways using semi-structured interviews. We will purposively sample participants across two categories: (1) participants with little to no engagement (bottom 50% of activity) and (2) participants with high levels of engagement (top 50% of activity) according to the user engagement data (e.g., # of texts that users sent per month, % of external link clicks) at month 3 of the RCT. We will plan to invite all participants with little to no engagement in an interview who have consented to being contacted to participate in the process evaluation. Semi-structured interviews will be informed by the HAPA and TAM and will explore how context influences intervention uptake and adherence among participants (please see Interview Guide 1). Specifically, we will explore the technological aspects (perceived usefulness, perceived ease of use), treatment aspects (perceived needs, outcome expectation, self-efficacy, etc.), and social aspects (social support, competing priorities, etc.) of the KiT intervention. For those who have high levels of engagement at three months, we will explicitly explore the interventions' mechanism of action as hypothesized in Step 1 (please see Interview Guide 2). Participants who complete the process evaluation interview, 45-60 minutes, will be compensated with a \$25 gift card for their time. In Step 3, we will identify the potential paths and corresponding combination of factors that are associated with trial outcomes using Coincidence Analysis.

Data to be transferred to THP for process evaluation:

1. Participant sampling
- Participant-level engagement data at months 1-3 of the RCT
- Demographic data
2. Participant recruitment
- Contact information (including name, phone number, and email address)
3. Data triangulation and analysis
- Study ID
- Participant-level engagement data at months 4-6 of the RCT
- RCT health outcome data (including SEDM, READDY, stigma, and HbA1c)

Data transfer for Process evaluation:

Sites will identify participants who consented to be contacted for an interview for the process evaluation. Sites will send study id, name and contact information (phone/email) to SickKids. SickKids will send study id, contact information (from sites) and engagement data (from Memotext) to THP via SickKids secure data transfer portal. THP research staff recruit and schedule interviews for those participants for the process evaluation.

9 STATISTICAL CONSIDERATIONS

8.2 STATISTICAL HYPOTHESES

- **Primary Endpoint(s):** Diabetes self-efficacy measured by SEDM at baseline, 6 and 12 months after baseline. We hypothesize that the intervention will improve engagement with support content and improve self-management of diabetes among the intervention group compared to control group at 12 months compared to baseline.
- **Secondary Endpoint(s):** transition readiness measured by the READDY tool; perceived stigma measured by the Barriers to Diabetes Adherence (BDA) stigma subscale, and time from final pediatric to first adult diabetes appointment; HbA1c; diabetes-related ED visits and hospitalizations at 12 months. We hypothesize that the intervention, may improve transition readiness and improve glycemic management, decrease the time from last pediatric to first adult diabetes appointment, and decrease the frequency of diabetes-related ED visits and hospitalizations in the intervention group compared to the control group at 12 months compared to baseline.
- **Exploratory Endpoint(s):**
 - Within the embedded process evaluation, we will investigate the pragmatic nature of this trial and study whether making real-time adjustments will improve user interaction and experience will increase user uptake and satisfaction. We will also identify the different paths of engagement (i.e., combinations of KiT components) that produce a positive effect on trial outcomes.
 - We will measure the cost of implementing this intervention to inform the feasibility of scaling this intervention.
 - We will explore if socioeconomic status as measured by material deprivation quintile is related to the use, engagement and effectiveness of the KiT intervention on diabetes self-

efficacy and/or the readiness to transition to adult diabetes care, and/or barriers to diabetes adherence stigma subscale.

8.3 SAMPLE SIZE DETERMINATION

The total sample size of 234 (117 per arm) was determined based on the number of adolescents with T1D who are annually transferred to adult diabetes care at each participating site:

- Ontario (4 sites total): The Hospital for Sick Children, Children's Hospital of Eastern Ontario (CHEO), Markham Stouffville Oaklands and Trillium Health Partners. The total number of patients annually transferred from these Ontario pediatric diabetes centers to adult diabetes centers is approximately 202. Thus, over an 21-month period, there will be approximately 303 patients transferred to adult diabetes care who are eligible to participate in this trial. We estimate, based on prior experience of the investigators involved in transition research, that we would be able to make contact, recruit, consent and enroll approximately half (152) of the eligible patients (303), and account for 20% (30) being lost to follow-up, we will have approximately 120 participants from Ontario sites enrolled in this trial.
- Quebec (2 sites total): Montreal Children's Hospital and CHU Saint Justine. The total number of patients annually transferred from both pediatric diabetes centers to adult diabetes centers is approximately 152. Thus, over an 21-month period, there will be approximately 228 patients transferred to adult diabetes care who are eligible to participate in this trial. We estimate, based on prior experience of the investigators involved in transition research, that we would be able to make contact, recruit and enroll approximately half (114) of the eligible patients (228), and account for 20% (23) being lost to follow-up, we will have approximately 90 participants from Quebec sites enrolled in this trial.

We have a conservative sample size of 234 (117 per arm) that will provide more than 80% power of detecting a between-group change in mean score for self-efficacy with diabetes management (SEDM) of 0.75, this accounts for 20% loss to follow-up at the 5% significance level (alpha) using a two-sample equal-variance t-test.

8.4 POPULATIONS FOR ANALYSES

The conventional frequentist analyses are often interpreted in a dichotomous matter, based on the p-value chosen as threshold for 'statistical significance' and 'no evidence of effect' is confounded with 'evidence of no effect'. A Bayesian analysis will be conducted to provide the probability of any benefit or harm. An intention-to-treat analysis will be conducted by blinded analysts. We will evaluate the extent of missing data to determine if values are missing at random or not and will consider imputation to account for missing values.

8.5 STATISTICAL ANALYSES

8.5.1 GENERAL APPROACH

Demographics and baseline characteristics will be summarised using descriptive statistics. Continuous data will be reported as means with SDs.

8.5.2 ANALYSIS OF THE PRIMARY ENDPOINT(S)

We will compare the mean SEDM score at 12 months between those in the intervention (regardless of original or modified) versus control arms. This will be done using linear regression to estimate the effect of the KiT intervention on self-efficacy of diabetes management, controlling for baseline SEDM. The linear model will be estimated using Bayesian linear mixed effect model accounting for the clustering of patients at their pediatric diabetes clinic using integrated nested Laplace approximation (INLA). We will adjust our analysis by sex and gender. The results will be presented as posterior mean with 95% creditable interval, probability of any benefit or any harm, and the probability of clinical important benefit. Any benefit is defined as the difference between two arms is greater than zero. Any harm is defined as the difference is smaller than zero. The threshold for clinical important benefit is chosen at 0.75. A significant probability of benefit or harm (clinical important benefit) will be declared above 95%.

Sensitivity analysis

Clinicians were uncertain about whether they would expected differences between the modified intervention and the original intervention. Therefore, we will also investigate the potential impact of the modified intervention compared to the original intervention. To determine this, we will perform a sensitivity analysis by examining the interaction effects between the original intervention and the number of months under the modified intervention. We use the same model as our primary analysis, adjusting for atreatment indicator (under the original intervention) and the interaction between being on treatment and the number of months exposed under the modified intervention. This analysis will allow us to understand the impact of the duration of exposure to the modified intervention. Our goal is to compare individuals who received the 12-month modified intervention and those who received the 12-month original intervention by leveraging the partially exposed data. The sensitivity analysis will involve the following steps:

- (1) Calculate the posterior probability of the difference between the estimated effect of receiving 12 months of the modified intervention and 12months of the original intervention being greater than zero. This will determine whether there is any evidence to support the idea that the modified intervention is more effective than the original intervention. If the probability is less than 90%, we can conclude that there is no significant evidence to prove the difference between the two interventions.
- (2) If the posterior probability calculated in step (1) is greater than 90%. We then use our interaction effect model to calculate the posterior probability of any benefit/harm and probability of clinical important benefit of receiving the 12-month original and 12-month modified interventions separately as a supplement to the primary analysis.

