4 STUDY DESIGN

4.1 OVERALL DESIGN

First, we **hypothesize** that the intervention will improve diabetes self-efficacy.

We will conduct a **multi-site randomized control trial** to evaluate the effectiveness of an eHealth solution for T1D transition care. The study sample size is 234 adolescents with T1D from 6 pediatric diabetes centres (4 in Ontario and 2 in Quebec) and allocate them 1:1 to the intervention or control arm stratified by site. Participants will be recruited at their pediatric centre within 3-4 months of either their planned final pediatric visit or 18th birthday. We opted for individual randomization the target of the intervention is diabetes self-efficacy during the time between pediatric and adult care and relates to the individual rather than provider or clinic-based practices.

Intervention: both intervention and control groups will receive usual diabetes care including all medical visits and tests. In addition, the intervention group will receive the text messages for diabetes support and resources tailored according to their needs and interest. Both intervention and control groups will also complete PREMs and PROMs at baseline, 6 and 12 months.

Process Evaluation: the embedded process evaluation involves a mixed-methods approach using individual semi-structured interviews alongside user engagement metrics and quantitative outcome data to evaluate how and why the intervention achieved (or failed to achieve) the desired effects and identifying the different paths of engagement (i.e., combinations of KiT components) that produce a positive effect on trial outcomes. Using an embedded single case design with cross case synthesis, the objective of the process evaluation is to gain an in-depth understanding of whether the intervention was received as intended (intervention fidelity), the mechanisms of action, and the conditions and factors associated with initial engagement and sustained use of the intervention.

Health system impact: We will examine health care utilization of patients with T1D using de-identified administrative and, self-reported health data for at least 12 months after study enrolment. We will securely link patients' health card number to provincial administrative databases housed at ICES in Ontario and Med-Echo and Régie de l'assurance maladie du Québec (RAMQ) databases in Quebec.

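### Does declaring benefit or harm at 95% posterior probability in section 8.5.2 conflict with the 95% credible interval beside it and the 5% alpha in section 8.3?

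*Protocol*

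**What the plan says.** Protocol section 8.4 explains the move away from reading results as significant or not by p-value and says: "A Bayesian analysis will be conducted to provide the probability of any benefit or harm".

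Section 8.5.2 then sets out the primary analysis:

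- Model: a Bayesian linear mixed model with baseline SEDM as covariate. The protocol names no prior for the treatment effect.
- Reporting: "The results will be presented as posterior mean with 95% creditable interval", together with the probabilities of any benefit, any harm and clinically important benefit.
- Definitions: benefit means that the arms differ by more than zero, harm that they differ by less than zero, and 0.75 is the cut-off for a clinically important benefit.
- Declaration: "A significant probability of benefit or harm (clinical important benefit) will be declared above 95" per cent.

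Section 8.3 claims more than 80% power for a difference of 0.75 with 117 per arm, and adds: "this accounts for 20% loss to follow-up at the 5% significance level (alpha) using a two-sample equal-variance t-test". It states neither the sidedness nor the SD. Section 4.1 gives a directional hypothesis, "that the intervention will improve diabetes self-efficacy".

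**The concern.** Three things seem not to fit together.

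1. An equal-tailed 95% credible interval excludes zero only when the posterior probability of one direction exceeds 97.5%. The declaration needs only 95%. One paragraph could therefore yield a declared benefit and an interval that includes zero.
2. The rule covers both directions. With little prior information each carries about 5% error under no effect, 10% in all. That is twice the total of a two-sided 5% test, which is how many readers would take the alpha in section 8.3.
3. The parenthesis in the declaration seems to put the same bar on the probability that the difference exceeds 0.75. That is also the sizing effect, so the power in section 8.3 would not apply to this declaration.

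If these were errors, the headline conclusion of the trial would rest on a looser standard than the one used to size it.

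**Working it through.** **Inputs.** From the protocol: 117 per arm, 20% loss, sizing difference and clinical threshold both 0.75, declaration bar 95%, interval 95%. Evaluable per arm: 117 × 0.8 = 93.6, taken as 94. Assumed, because the protocol does not give them: the SD of SEDM, the prior, and a baseline correlation of 0.5 where adjustment is considered.

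**The plan's own figure.** The power above 80% can be neither confirmed nor refuted without an SD. With 94 per arm, a t-test has exactly 80% power at 0.75 if the SD is 1.83 (two-sided 5%) or 2.06 (one-sided 5%). Unless noted, SD 1.83 is used below; a smaller SD makes the effects smaller.

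**Standard error.** SE = SD × √(2/n) = 1.83 × √(2/94) = 0.267. With baseline correlation 0.5, SE = 0.267 × √(1 − 0.25) = 0.231.

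**Error rate with no effect.** Under a flat prior the posterior probability of benefit is Φ(z), so the 95% bar means z > 1.645: 5% for benefit, 5% for harm, 10% in total. A simulation of 200,000 null trials (93 per arm, SD 1.8) gave 4.9%, 5.0% and 9.9%. With a normal prior centred at zero with SD τ, the total is 2 × [1 − Φ(1.645/√w)], where w = τ²/(τ² + SE²):

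| Prior SD τ | Total, both directions |
|---|---|
| flat | 10% |
| 2 | 9.7% |
| 1 | 8.9% |
| 0.5 | 6.2% |
| 0.375 | 4.4% |

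So the total depends on a prior that the protocol does not fix.

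**Bar against interval.** This gap holds under any prior: results with posterior probability between 95% and 97.5% are declared while the equal-tailed 95% interval includes zero. Under a flat prior the observed differences concerned run from 1.645 × 0.267 = 0.44 to 1.96 × 0.267 = 0.52 (0.38 to 0.45 with baseline adjustment).

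**Power at a true 0.75.**

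| | 95% bar | 97.5% bar |
|---|---|---|
| SD 1.83, unadjusted | 0.878 | 0.802 |
| SD 1.83, correlation 0.5 | 0.945 | 0.900 |
| SD 2.06, unadjusted | 0.802 | 0.704 |
| SD 2.06, correlation 0.5 | 0.892 | 0.822 |

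The share of trials in the gap at SD 1.83 is 0.878 − 0.802 = 0.076, about 8% (0.945 − 0.900 = 0.045 with adjustment). At SD 1.5, SE = 0.219 and the unadjusted share is about 3%.

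**Clinically important benefit.** If the parenthesis applies the 95% bar to a difference above 0.75, the rule succeeds 5% of the time at a true 0.75 under a flat prior. It reaches 80% at 0.75 + (1.645 + 0.842) × 0.267 = 1.41, or 1.32 with baseline adjustment.

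**The case for a change.** The strongest case for a change is that the gap between bar and interval needs no SD, no prior and no frequentist reasoning, and that the 95% bar, the 95% interval and the 5% alpha are all fixed in the protocol, not left to the SAP. Section 8.5.2 speaks of significance although section 8.4 objects to dichotomous reading. Section 10.1.1 also lists the primary endpoint having been met as a possible reason to terminate, so the meaning of met should be clear.

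The mathematics of this stands. The step from there to an error does not.

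- The interval and the directional probability summarise one posterior. Section 8.5.2 ties the declaration to the probability and gives the interval no deciding role. A 96% probability of benefit with a 95% interval just reaching below zero is an accurate account of moderate evidence.
- Section 8.3 attaches its 5% to the t-test used for sizing. No passage promises that the posterior rule keeps total error at 5%. The sensitivity analysis in section 8.5.2 uses a 90% bar, so these bars are not presented as equivalents of alpha.
- The 10% adds two different mistakes. The chance of a false claim of efficacy is 5%, in line with a one-sided 5% test of the directional hypothesis in section 4.1.
- The rule for what counts as met is numeric and set in advance. The interim analysis in section 8.5.5 concerns engagement and satisfaction only, so it adds no extra look at SEDM.
- Section 8.3 claims power to detect a difference of 0.75, not to show that the true difference exceeds 0.75. About 5% success when the margin equals the truth is what such a rule must give.

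**Conclusion.** The concern does not call for a change. Under a weak prior the declaration carries about 5% error per direction and corresponds to a 90% interval, but this contradicts no figure or rule in the protocol. The stated power is not overstated: at SD 1.83 the 95% bar gives about 88% for any benefit at a true 0.75. The conflict in appearance is confined to observed differences of about 0.44 to 0.52 unadjusted, under a flat prior.

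A 97.5% bar would make the declaration agree with the 95% interval, but it would lower power from 88% to 80%, or from 80% to about 70% if the 5% in section 8.3 was one-sided and the SD is 2.06 (unadjusted). Statisticians could reasonably choose either bar. Stating the sidedness, quoting the error rate per direction under the chosen prior, adding a 90% interval, or spelling out the parenthesis would record or present the same result and would not correct one. The prior and its operating characteristics commonly belong in the SAP, which is not at hand. Because the probabilities and the interval are reported together, readers can weigh a borderline result themselves.

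These sizes rest on 94 evaluable per arm, an assumed SD, and a flat prior except where a prior SD is given.
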